7.2 Sample Size and Power

This is a rollover study that plans to enroll subjects from qualifying previous studies (Study 109 and Study 011B) who meet the inclusion and exclusion criteria for this study. Approximately 256 subjects are potentially eligible to be enrolled into Study 110: approximately 200 subjects from Study 109 and approximately 56 subjects from Study 011B. Table 7-1 provides the 95% Confidence Intervals (CIs) for observing the CF lung events assuming different incidence of CF lung (i.e., pulmonary exacerbation) in CF subjects.

Table 7-1 95% CIs Assuming Different Observed Incidences of CF lung

Observed CF lung incidence	95% CI (n=256)
0.1	(0.063, 0.137)
0.2	(0.151, 0.249)
0.3	(0.244, 0.356)
0.4	(0.340, 0.460)

7.3 Randomization

This is an open-label study. No randomization is planned.

7.4 Blinding and Unblinding

This is an open-label study; however, subjects and their parent/caregiver should not be informed of their study-related LCI, spirometry, sweat chloride, [REDACTED] results until all Treatment Cohort Period 1 subjects complete Treatment Cohort Period 1, regardless if the subject has prematurely discontinued from Study 110 Treatment Cohort Period 1 or not.

8 ANALYSIS SETS

Enrolled subjects are those who signed informed consent/assent form and had an enrollment date on the CRF. For Treatment Cohort Period 2 and Observational Cohort, all summaries will be based on all enrolled subjects from the corresponding cohort.

All Subjects Set includes all subjects randomized or dosed in Study 109 and all subjects enrolled or dosed in Study 011B.

110 All Subjects Set includes all subjects enrolled or dosed in Study 110 Treatment Cohort Period 1.

8.1 Efficacy Set

Full Analysis Set (FAS) includes all subjects who are randomized and dosed in Study 109, or subjects enrolled and dosed in Study 011B. The FAS treatment group assignment is shown in Table 8-1; the treatment group will be as randomized/enrolled in the previous studies.

Table 8-1 FAS Treatment Group Assignment in Study 110

Treatment Groups	Description
L200/I-L/I	Subjects randomized/enrolled to L200/I in the previous studies (Study 109 or Study 011B) ^a
P-L/I	Subjects randomized to placebo in Study 109 ^a

I: ivacaftor; L: lumacaftor; P: placebo.

^a Subjects who turn 12 years of age in the previous studies or Day 1 of this rollover study will begin receiving L400/I on Day 1. Subjects who turn 12 years of age after the Day 1 Visit of this rollover study will begin receiving L400/I at their next scheduled visit.

110 Full Analysis Set (110 FAS): The 110 FAS will include all subjects who rolled over from Study 109 and Study 011B, and who are enrolled and exposed to any amount of study drug in Study 110. The 110 FAS treatment group assignment is shown in Table 8-2; the treatment group will be as randomized/enrolled in the previous studies.

Table 8-2 110 FAS Treatment Group Assignment in Study 110

Treatment Groups	Description
L200/I-L/I	Subjects randomized/enrolled to L200/I in the previous studies (Study 109 or Study 011B) and enrolled and dosed in Study 110 ^a
P-L/I	Subjects randomized to placebo in Study 109 and enrolled and dosed in Study 110 ^a

I: ivacaftor; L: lumacaftor; P: placebo.

^a Subjects who turn 12 years of age in the previous studies or Day 1 of this rollover study will begin receiving L400/I on Day 1. Subjects who turn 12 years of age after the Day 1 Visit of this rollover study will begin receiving L400/I at their next scheduled visit.

109 Full Analysis Set (109 FAS): The 109 FAS will include all subjects who are randomized and exposed to any amount of study drug in Study 109.

109 Rollover Set (109 ROS): The 109 Rollover Set will include subjects who rolled over from Study 109 (enrolled in Study 110) and were exposed to any amount of study drug in Study 110.

8.2 Safety Set

Safety Set includes all subjects who are exposed to any amount of study drug in the previous studies. The treatment group will be as treated in the previous studies. The Safety Set treatment group assignment is shown in Table 8-3. For subjects who received study drug from both of the placebo and active treatment groups in Study 109, the treatment group allocation for as-treated analysis will be the L200/I-L/I group.

Table 8-3 Safety Set Treatment Group Assignment in Study 110

Treatment Groups	Description
L200/I-L/I	Subjects dosed with any L200/I in the previous studies (Study 109 or Study 011B)
P-L/I	Subjects dosed with placebo only in Study 109

I: ivacaftor; L: lumacaftor; P: placebo.

^a: Subjects who turn 12 years of age in the previous studies or Day 1 of this rollover study will begin receiving L400/I on Day 1. Subjects who turn 12 years of age after the Day 1 Visit of this rollover study will begin receiving L400/I at their next scheduled visit.

110 Safety Set: The 110 Safety Set will include all subjects dosed in previous studies who are exposed to any amount of study drug in Study 110. The 110 Safety Set treatment group assignment is shown in Table 8-4. For subjects who received study drug from both of the placebo and active treatment groups in Study 109, the treatment group allocation for as-treated analysis will be the L200/I-L/I group.

Table 8-4 110 Safety Treatment Group Assignment in Study 110

Treatment Groups	Description
L200/I-L/I	Subjects dosed with any L200/I in the previous studies (Study 109 or Study 011B) and dosed in Study 110 ^a
P-L/I	Subjects dosed with placebo only in Study 109 and enrolled and dosed in Study 110 ^a

I: ivacaftor; L: lumacaftor; P: placebo.

^a Subjects who turn 12 years of age in the previous studies or Day 1 of this rollover study will begin receiving L400/I on Day 1. Subjects who turn 12 years of age after the Day 1 Visit of this rollover study will begin receiving L400/I at their next scheduled visit.

8.3 Other Analysis Set

All subjects from Study 109 and subjects from Study 011B LCI substudy will undergo LCI assessments in Study 110, the following analysis sets are defined to provide related summaries:

LCI Set is a subset of the FAS including the 109 FAS subjects and the FAS subjects from Study 011B who consent to the Study 011B LCI Substudy.

110 LCI Set is a subset of the LCI Set including subjects in the LCI Set who enrolled and exposed to any amount of study drug in Study 110.

9 ANALYSIS PERIODS

9.1 Treatment Cohort Period 1

Three different Study Periods, as detailed below, will be defined and analyzed for Treatment Cohort Period 1 subjects. The safety analysis for the corresponding Study Period will be based on its treatment-emergent period.

9.1.1 Previous Study Period

Previous Study Period starts from the first dose date of study drug in the parent studies (109 and 011B) to up to the first dose date of study drug in Study 110, including 1) the planned 2-week washout period per Study 011B design; or 2) the Roll-Over Gap between the previous studies (Study 109 and Study 011B) and Study 110.

For the majority of the subjects, the first dose of study drug and assessments in Study 110 will happen on the same day as the Week 24 Visit in Study 109 or the Week 26 Visit in Study 011B.

For assessment performed on the first dose day in Study 110:

- If information regarding the assessment timing is available, then the assessment time will be compared to the first dose time in Study 110 to decide whether the assessment is before the first dose, concurrent with the first dose, or after the first dose.
- If information regarding assessment timing is not available, then the record will be included in the Previous Study Period if it comes from the Previous Study database, and the record will be included in the Current Study Period if it comes from the Current Study database.

Treatment-Emergent Period for the Previous Study Period

The treatment-emergent period for the Previous Study Period is the period on or after the first dose of study drug in the previous studies to 28 days after the last dose of the previous studies, or the last day of the Previous Study Period, or up to the first dose date in Study 110 (not including the first dose date in Study 110), whichever occurs first, for subjects dosed in Study 110.

For subjects not dosed in Study 110, the treatment-emergent period will be the period on or after the first dose of study drug in the previous studies to 28 days (inclusive) after the last dose of study drug in the previous studies or to the last day in the previous studies (inclusive), whichever occurs first.

9.1.2 Current Study Period

Current Study Period starts from the first dose date of study drug in Study 110 to the last day in Study 110.

Treatment-Emergent Period for the Current Study Period

The treatment-emergent period for the Current Study Period is the period on or after the first dose of study drug in Study 110 to 28 days (inclusive) after the last dose of study drug in Study 110 or up to the last day in Study 110, whichever occurs first.

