9.1.3 Cumulative Study Period

Cumulative Study Period starts from the first dose of study drug in the parent studies (109 and 011B) to the last day in Study 110, regardless of whether there is 1) the planned 2-week washout period per Study 011B design; or 2) a Roll-Over Gap between the previous studies (Study 109 and Study 011B) and Study 110. For subjects not enrolled in Study 110, the Cumulative Study Period will be the same as the Previous Study Period.

Treatment-Emergent Period for the Cumulative Study Period

The treatment-emergent period for the Cumulative Study Period is the period on or after the first dose of study drug in the previous studies to 28 days (inclusive) after the last dose of study drug in Study 110, or up to the last day in Study 110, whichever occurs first. For subjects not enrolled in Study 110, the treatment-emergent period for the Cumulative Study Period will be the same as that of the Previous Study Period.

Handling of the data during the gap between previous studies (Study 109 and Study 011B) and the rollover study (Study 110)

There may be a Roll-Over Gap between the previous studies and the rollover study, defined as the time period between the Week 24 Visit of Study 109 or the Week 26 Visit of Study 011B and the date prior to the Day 1 Visit of Study 110. All analyses will be performed regardless of whether there is a Roll-Over Gap between the previous studies (Study 109 and Study 011B) and Study 110.

- This affects summary of the following possibly continuing events: 1) AEs; 2) CMs; and 3) Pulmonary Exacerbation related endpoints: Pulmonary Exacerbations, Pulmonary Exacerbations requiring hospitalizations (planned and unplanned), and Pulmonary Exacerbations requiring IV antibiotics.

Events that happen during the Roll-Over Gap will be included in the Cumulative Study Period related analysis, but not necessarily in the analysis of the previous studies or the Current Study Period for Study 110. There are possible differences between results from Cumulative Study Period and combining results from previous studies and the Study 110.

- The Roll-Over Gap will not be considered in the derivation of the analysis window. The assessments will be selected per windowing rules specified for visits in Study 110 as described in Appendix D. The same set of selected records will be associated with different visit labels for different dosing periods.

9.2 Treatment Cohort Period 2

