Treatment-Emergent Period for the Treatment Cohort Period 2

For Treatment Cohort Period 2 subjects, safety analysis will be based on the treatment-emergent period, which starts from the Study 110 Week 96 dose date +1, or Week 96 visit date +1,

whichever occurs later; up to 28 days (inclusive) after the last dose of this dosing period, or the last available date in Study 110 Treatment Cohort Period 2, whichever occurs first.

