10 STATISTICAL ANALYSIS

10.1 General Considerations

In later sections, for analysis related to FAS, Safety Set, LCI Set [REDACTED] in Treatment Cohort Period 1, the population will not be limited to subjects in Treatment Cohort Period 1, regardless of the subtitle “Treatment Cohort Period 1”. The analysis will strictly follow their definitions in Section 8 of the SAP.

For subjects in the Observational Cohort, summaries will only be provided for the disposition, demographic and baseline characteristics, and SAEs. Summaries will be provided based on all enrolled subjects in the Observational Cohort.

For subjects in the Treatment Cohort Period 2, summaries will only be provided for the disposition, demographics, AEs, SAEs, LFTs, and ophthalmologic examinations analyses.

The Schedule of Assessments is provided in Appendix A.

Treatment Cohort Period 1

For Treatment Cohort Period 1, all analyses will be provided using all available data, regardless of whether subjects turned 12 years of age and subsequently switched to the higher dose with LUM 400 mg q12h/IVA 250 mg q12h.

The efficacy and safety analysis for different Study Periods will be based on different analysis set as summarized in Table 10-1.

Table 10-1 Analysis of Efficacy and Safety Based on Different Analysis Set in Different Study Periods

Period	Efficacy			Safety
Previous/Cumulative Study Period	FAS	109 FAS	LCI Set	Safety Set
Current Study Period	110 FAS	109 ROS	110 LCI Set	110 Safety Set

Continuous variables will be summarized using the following descriptive summary statistics: the number of subjects (n), mean, standard deviation (SD), standard error (SE), median, minimum value (min), and maximum value (max). Precisions of the summary for continuous variables are detailed in Table 13-4, Appendix B.

Categorical variables will be summarized using counts and percentages. Percentages will be presented to 1 decimal place.

Baseline: The baseline value of each Study Period for the Treatment Cohort Period 1 is defined as the most recent measurement (scheduled or unscheduled) before intake of the first dose of the corresponding Study Period, except if specified otherwise. These baselines are referred to as previous study baseline, current study baseline and cumulative study baseline.

- For LCI-related parameters, the values at each visit will be calculated based on the multiple replicates per the algorithm provided by the LCI central reader as detailed in Appendix C.

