10.2 Background Characteristics

10.2.1 Subject Disposition

Treatment Cohort Period 1

Number of subjects in the following categories will be summarized and tabulated:

- 110 All Subjects Set
- 110 FAS
- 109 ROS
- Subjects enrolled in Treatment Cohort Period 1 but never dosed

The number and percentage of subjects in each of the following disposition categories in Study 110 Treatment Cohort Period 1 for the Current Study Period will be summarized with the number in 110 FAS as the denominator:

- Completed treatment in Treatment Cohort Period 1
- Prematurely discontinued the treatment and the reasons for discontinuations
 - Last completed scheduled on-treatment assessment

- Completed Study 110 Treatment Cohort Period 1
- Prematurely discontinued the study in Treatment Cohort Period 1 and the reasons for discontinuations

Subject disposition will be summarized similarly with the number of subjects in 110 Safety Set as denominator for the Current Study Period.

Disposition table will also be provided based on 110 LCI Set and 110 [REDACTED]. A separate table summarizing the following analysis population will also be provided:

- All Subjects Set
- Safety Set
- FAS
- 109 FAS
- LCI Set

- All Enrolled Subjects for Treatment Cohort Period 1

Subject enrollment by region, country and by site will be summarized in a separate table based on all subjects enrolled into Study 110 Treatment Cohort Period 1.

A listing will be provided for subjects who discontinued treatment or who discontinued Study 110 in Treatment Cohort Period 1 with reasons for discontinuation.

Observational Cohort

Number and percentage of subjects in the following categories will be summarized:

- Enrolled in Study 110 Observational Cohort (overall, by region, country and by site)
- Completed Long-term Follow-up Visits (telephone contacts)
- Prematurely discontinued the study during the Long-term Follow-up and the reasons for discontinuations

Treatment Cohort Period 2

The number and percentage of subjects in each of the following disposition categories in Study 110 Treatment Cohort Period 2 will be summarized with the number of subjects enrolled in Treatment Cohort Period 2 as the denominator.

- Enrolled in Study 110 Treatment Cohort Period 2 (overall and by site)
- Enrolled and dosed in Study 110 Treatment Cohort Period 2
- Enrolled in Study 110 Treatment Cohort Period 2 but never dosed
- Completed treatment in Treatment Cohort Period 2

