10.2.4 Study Drug Exposure

Treatment Cohort Period 1

Study drug exposure will be summarized for the Previous Study Period based on Safety Set, for the Current Study Period based on 110 Safety Set, and for the Cumulative Study Period based on Safety Set.

Duration of exposure is defined as: last available dose date of the Study Period – first dose date of the same Study Period + 1 day, regardless of 1) unplanned interruptions, 2) the Roll-Over Gap between Previous Study and Study 110 and 3) the 2-week planned wash-out period for subjects from Study 011B for the summary of study drug exposure for the Cumulative Study Period. Duration/cumulative duration of study drug exposure will be summarized descriptively as a quantitative variable (number, mean, SD, SE, median, min, and max) for:

- Previous Study Period (Studies 109/011B) based on Safety Set with two treatment groups (L200/I, Placebo);
- Current Study Period (Study 110) based on 110 Safety Set with two treatment groups (L200/I-L/I, P-L/I) and Overall;
- Cumulative Study Period based on Safety Set with L200/I-L/I, and Current Study Period based on 110 Safety Set with P-L/I, pooled together. The pooled treatment group is presented as L/I Overall.

Additionally, the total duration of study drug exposure, defined as the sum of the subject's duration of treatment exposure and expressed in patient years, will be provided.

Duration/cumulative duration of exposure will also be summarized as a categorical variable: ≥ 1 dose of study drug to <24 weeks, ≥ 24 to <48 weeks, ≥ 48 to <72 weeks, ≥ 72 to <96 weeks, ≥ 96 weeks to 120 weeks, and ≥ 120 weeks.

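### SAP 9.1.2 and 9.1.3 end the Current and Cumulative Study Periods at the end of Study 110 rather than of Treatment Cohort Period 1, so for Period 2 entrants the written rule runs past Week 96

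*SAP*

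**What the plan says.** SAP 9.1 opens with "Three different Study Periods, as detailed below, will be defined and analyzed for Treatment Cohort Period 1 subjects". The end rules then name the whole study:

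- 9.1.2: "Current Study Period starts from the first dose date of study drug in Study 110 to the last day in Study 110". Its treatment-emergent window closes at "28 days (inclusive) after the last dose of study drug in Study 110 or up to the last day in Study 110, whichever occurs first" (same section).
- The counterpart rule in section 9.1.3 reads "Cumulative Study Period starts from the first dose of study drug in the parent studies (109 and 011B) to the last day in Study 110". Its treatment-emergent window has the same end.
- 9.2: Period 2 has its own treatment-emergent window, "which starts from the Study 110 Week 96 dose date +1, or Week 96 visit date +1", whichever is later.

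These periods feed later sections. In 10.3.2.2.2 the negative binomial offset is the log of the time from first dose to the end date of the Study Period. The annualized exacerbation rate divides by total exposure in the period, and Kaplan-Meier censoring falls at the end of the analysis period. In 10.2.4, "Duration of exposure is defined as: last available dose date of the Study Period" sets where exposure stops.

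Other text points to Period 1 only. Disposition (10.2.1) refers to "disposition categories in Study 110 Treatment Cohort Period 1 for the Current Study Period". Sections 10.3.2 and 10.3.2.2.2 confine the secondary and other secondary analyses to Period 1. Section 10.5 gives the Period 1 Cumulative Study Period and Period 2 separate cutoffs. For Period 2, section 10.1 says "summaries will only be provided for the disposition, demographics, AEs, SAEs, LFTs, and ophthalmologic examinations analyses", a list without exacerbations. Figure 7-1 footnote d and Table 13-1 footnote c make Week 96 the start of Period 2.

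**The concern.** Period 2 is part of Study 110: SAP 9.2 and Appendix I both name it so. For a French subject who continues, the last day and last dose in Study 110 can be as late as Week 168. The period definitions therefore conflict with the scope statements, and a programmer who follows the definitions gets a different result from one who follows the scope.

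Two things are at stake.

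- **Safety.** The Current and Cumulative windows would overlap the Period 2 window. Adverse events and liver-test threshold results from Period 2 would then appear in both sets of tables (10.4.1, 10.4.2).
- **Exacerbation rate.** Exacerbations are documented at the visits in Appendix A. Table 13-1 has a row for them (other events related to outcome, Study 109 subjects). Table 13-2 shows no such row. It also shows no concomitant-medication row, although the definition rests on new or changed antibiotics. Period 2 time would enter the denominator without scheduled capture of the numerator, which biases the L200/I-L/I and P-L/I rates downward, in the favourable direction.

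**Working it through.** The plan gives no figure of its own on this point. The 95% intervals in SAP Table 7-1 do not bear on it.

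**Inputs**
- Period 1 ends at Week 96 and Period 2 at Week 168 (Tables 13-1 and 13-2), so Period 2 lasts at most 168 − 96 = 72 weeks.
- One patient-year is 48 weeks (SAP 10.1.2.1), so 72 weeks = 1.5 patient-years.
- P-L/I uses the Current Study Period: 96 weeks. L200/I-L/I uses the Cumulative Study Period: 24 + 96 = 120 weeks.
- Subjects who turn 12 in Period 2 leave the study (SAP 7.1).
- The share f of Study 109 subjects entering Period 2 is not in the documents. I assume f = 10% for illustration; f = 0 is possible and gives no effect on the exacerbation rates.

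**Per entrant.** P-L/I goes from 96 to 168 weeks (×1.75). L200/I-L/I goes from 120 to 192 weeks (×1.60).

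**Pooled rate.** If everyone completes 96 or 120 weeks, the 4-week follow-up is ignored and no Period 2 exacerbation is captured, then fall = 1 − 1/(1 + f × w/base), where w is the mean number of weeks spent in Period 2.
- w = 72, P-L/I: 0.1 × 72/96 = 0.075; fall = 0.075/1.075 = 7.0%.
- w = 72, L200/I-L/I: 0.1 × 72/120 = 0.060; fall = 0.060/1.060 = 5.7%.

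**Allowing for subjects who turn 12.** Assume ages uniform from 6 to under 12 at parent-study baseline. Week 96 is 120 weeks (840 days) later. The time left to age 12 among those still under 12 is then uniform on 0 to 6 × 365.25 − 840 = 1351.5 days. With a cap of 504 days (72 weeks), the mean Period 2 time is 504 − 504²/(2 × 1351.5) = 410 days, about 59 weeks (58.6).
- P-L/I: 0.1 × 58.6/96 = 0.0610; fall = 0.0610/1.0610 = 5.75%.
- L200/I-L/I: 0.1 × 58.6/120 = 0.0488; fall = 0.0488/1.0488 = 4.7%.

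**Negative binomial model.** With large overdispersion the estimate tends to the average of the subjects' own rates, so the fall tends to f × 72/168 = 4.3% (P-L/I) or f × 72/192 = 3.8% (L200/I-L/I). The planned model therefore moves less than the pooled rate as overdispersion grows.

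**Sensitivity to completion.** L200/I-L/I uses the 109 FAS, which includes subjects who never rolled over. If 10% contribute only 24 weeks (assumed), base = 0.9 × 120 + 0.1 × 24 = 110.4 weeks. With w = 72, the fall is 7.2/(110.4 + 7.2) = 6.1%, above the 5.7% found under full completion.

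**What does not move.** The placebo-period rate and the percentage with at least one exacerbation do not change. Nor do Kaplan-Meier estimates before about Week 96 (P-L/I) or Week 120 (L200/I-L/I). Visit-based efficacy is protected because the Week 96 windows in Table 13-5 close at Day 687. Events per 100 patient-years for adverse events are partly protected, since events and exposure grow together; the percentage of subjects with an event is not.

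**The case against.** The strongest reply is that the SAP already bounds these periods. The definitions sit under a Period 1 heading, Period 2 has its own section, and 10.3.2.2.2 limits the exacerbation analyses to Period 1. Figure 7-1 footnote d and Table 13-1 footnote c place the boundary at Week 96. This largely stands as evidence of intent. A reader might infer that the SAP gives no way to find the end of Period 1; that goes too far, because Week 96 can be derived. Nor does the waived Safety Follow-up Visit (Table 13-1 footnote d) show a missing closing visit: entrants continue treatment, and Week 96 closes Period 1 for them.

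The reply does not remove the conflict. Scope statements do not amend an explicit end rule that names Study 110. Reading Study 110 as Period 1 is also not enough: unless the last day of Period 1 is defined, last dose plus 28 days overlaps by up to 28 days a Period 2 window that opens the day after Week 96.

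Two further objections are fair. The SAP is based on Protocol Version 2.1, and the protocol supplied has no Period 2, so a clearer rule or exacerbation collection in the French version cannot be ruled out. Period 2 also collects adverse events continuously, so an exacerbation could appear there, though not against the protocol definition.

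**Conclusion.** The point holds as a contradiction between the written end rule and the SAP's own scope and Week 96 boundary. Severity is minor. The exacerbation rate is an other secondary endpoint, P values are nominal (10.3.2.3), no between-group efficacy comparison is planned (10.3.2.2.1), and the intent is probably Period 1 only.

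A reader might infer that the long-term exacerbation rates will be materially understated, or that the percentages above are upper limits. The documents support neither. They do not say how many Study 109 subjects entered Period 2, or that any did. The percentages rest on an assumed 10% share and full completion; early exit at age 12 lowers them, and non-completers in the 109 FAS raise them. What can be said is the direction (downward) and the per-subject maximum (72 weeks, 1.5 patient-years). The double counting of Period 2 safety events applies to any entrant, from either parent study, if the rule is followed literally.

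**What to change.** In SAP 9.1.2 and 9.1.3, replace *in Study 110* with *in Treatment Cohort Period 1* wherever the last day and the last dose are defined. Add one derivation rule: for subjects entering Period 2, the Study Periods, their treatment-emergent windows, exposure, the exacerbation offset and the Kaplan-Meier analysis period all end at the later of the Week 96 dose date and the Week 96 visit date. That meets the 9.2 start with no gap and no overlap. The cost is one phrase in two sections and one programming rule; no new data are needed.
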